9.5.1. Efficacy Analyses

Efficacy analyses will be performed using the FAS, mITT Set, and PP Set, and participants will be included in the study intervention group to which they are randomized.

9.5.1.1. Analysis of Primary Efficacy Endpoint

To assess the efficacy endpoint for the primary objective, preventing the first occurrence of RT-PCR confirmed protocol-defined ILI within the period of 14 days post study intervention through the end of the influenza season, Cox proportional hazards regression model will be used to estimate HR. The rVE, ie, 1-HR (mRNA-1010 vs. active comparator) will be estimated along with the 2-sided 95% CI and 1-sided *p-value* for testing $H_0^1: rVE \leq -10\%$.

The rVE is defined as the percent reduction in the hazard of the primary endpoint (mRNA-1010 vs. active comparator) and will be estimated using 1-HR estimand. A stratified Cox proportional hazard model with study intervention group as a fixed effect will be used based on the PP Set to estimate the HR (mRNA-1010 vs. active comparator). The stratification factors at randomization, ie, age group (≥ 50 to < 65 years or ≥ 65 years) and influenza vaccine status in the previous season (received or not received), will be applied as the strata variables. The Efron's method will be used to handle ties.

For the primary efficacy endpoint, participants without RT-PCR confirmed protocol-defined ILI will be censored at the last study assessment date. Potential intercurrent events may include:

1. Early discontinuation or death unrelated to influenza; or
2. Early ILI up to 14 days after study intervention.

In the estimand of the primary analysis on the primary endpoint, a hypothetical strategy will be used to address the intercurrent events in the primary analysis based on the PP Set. The details are presented in [Section 11.3](#).

Participants without RT-PCR confirmed protocol-defined ILI will be censored at Day 181 (Month 6) or end of influenza season (whichever occurs later), or at the date of early discontinuation or death unrelated to influenza, whichever is earlier. Participants with early RT-PCR confirmed protocol-defined ILI up to 14 days after the study vaccination will be censored at the start date of the early RT-PCR confirmed protocol-defined ILI (see [Section 11.6](#) for country-specific amendment affecting this paragraph).

The trial will be considered to meet the primary efficacy objective if the *p-value* for rejecting $H_0^1: rVE \leq -10\%$ is less than the nominal *p-value* based on the Lan-DeMets Pocock boundaries, on the PP Set. The nominal alpha at the IA and final analysis will be 2.07% at IA and 1.2% at final analysis.

Analyses of the primary endpoint will be also performed based on the mITT Set using the same methods as described above.

To support the primary analysis, rVE will also be estimated by 1 minus the ratio of incidence rates adjusting for person-time, and the 95% CI of rVE will be computed using the exact method, conditional upon the total number of cases adjusting for person-time.

In addition, Kaplan Meier curve will be used to plot the estimated cumulative incidence rates over time by vaccine group. Participants without a case for the primary endpoint identified will be censored at Day 181/Month 6 or end of influenza season, whichever ends later.

Once the noninferiority of mRNA-1010 vs. active comparator is demonstrated using the PP Set, superiority of mRNA-1010 vs. active comparator will be evaluated using the same endpoint on the mITT Set, either at an IA or at the final analysis.

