7.2. Lost to Follow up

A participant will be considered Lost to Follow-up (LTFU) if the participant repeatedly fails to return for scheduled visits without stating an intention to withdraw consent and is unable to be contacted by the study site. The following actions must be taken if a participant fails to return to the clinic for a required study visit:

- The site must attempt to contact the participant and reschedule the missed visit as soon as possible, counsel the participant on the importance of maintaining the assigned visit schedule and ascertain whether the participant wishes to and/or should continue in the study.
- Before a participant is deemed lost to follow up, the Investigator or designee must make an effort to regain contact with the participant (where possible, 3 telephone calls and, if necessary, a certified letter to the participant's last known mailing address or locally equivalent methods). These contact attempts (eg, dates of telephone calls and registered letters) should be documented in the participant's medical record.
- Should the participant continue to be unreachable, the participant will be considered to have withdrawn from the study.
- A participant should not be considered LTFU until due diligence, as described above, has been completed.

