11.3. APPENDIX 3: Estimands and Estimand Specifications

Table 9: Intercurrent Event Types

Label	Intercurrent Event Type	Comment
IcEv1 (early discontinuation or death without confirmation of cases, ie, unrelated death)	Unrelated death without documented influenza	Participants in PP Set who withdraw consent or die due to reasons unrelated to influenza will be included in primary efficacy analysis.
IcEv2 (early infection)	Infection starting up to 14 days after the study intervention	Participants in PP Set who experience an early influenza infection up to 14 days after the IP will be included in primary efficacy analysis.
Abbreviation: IcEv: intercurrent event, PP: per-protocol, FAS: full analysis set, mITT: modified intent-to-treat.		

Table 10: Primary Objective and Estimands with Rationale for Strategies to Address Intercurrent Events for Per-Protocol Analysis

Objective: To demonstrate the efficacy of mRNA-1010 to prevent influenza	
Estimand Description	Vaccine efficacy will be measured using 1 – HR (mRNA-1010/Fluarix) from 14 days after study intervention. A hypothetical strategy will be used for early discontinuation (eg, withdrawal consent, deaths unrelated to influenza) or early infection in participants in PP Set.
Target Population	Adults aged 50 years and older
Variable/Endpoint	Time to first episode of RT-PCR confirmed protocol-defined ILI, censoring at early discontinuation, early infection, or last assessment for an event not being observed, whichever comes earlier.
Treatment Condition(s)	Test: mRNA-1010 Reference: Active Comparator (Fluarix®)
Estimand Label	Estimand 1
Population-Level Summary	Vaccine efficacy defined as 1 - HR of mRNA-1010/active comparator
Intercurrent Event Strategy	
IcEv1 (Early discontinuation or unrelated death):	Hypothetical
IcEv2 (early infection):	Hypothetical
Rationale for Strategy(s)	Hypothetical: early discontinuation (including unrelated death) censored at time of discontinuation (or at time of death), and early case will be censored at the time at case onset, handled with independent censoring.

Abbreviation: HR = Hazard ratio; IcEv: intercurrent event; ILI = Influenza like illness; RT-PCR = Reverse transcription polymerase chain reaction

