Participants without RT-PCR confirmed protocol-defined ILI will be censored at Day 181 (Month 6) or the end of the influenza season (whichever occurs later), or at the data cutoff date for interim analysis, or at the date of early discontinuation or death unrelated to influenza, whichever is earliest. Participants with early RT-PCR confirmed protocol-defined ILI up to 14 days after the study vaccination (i.e., start date of the RT-PCR confirmed ILI \leq vaccination date +13) will be censored at the start date of the early RT-PCR confirmed protocol-defined ILI.

The trial will be considered to meet the primary efficacy objective by demonstrating NI of mRNA-1010 to the active comparator if the one-sided p-value for rejecting $H_0^1: HR \geq 1.1$ (equivalently, $H_0^1: rVE \leq -10\%$) is less than the nominal alpha based on the Lan-DeMets Pocock approximation spending function, based on the PP Set. The nominal one-sided alpha level will be 2.07% at IA, and 1.2% at the final analysis, respectively, if the IA is conducted when exactly 75% of the total number of cases are observed.

As sensitivity analyses, the primary endpoint analysis for NI will be repeated on the mITT Set using the same methods as described above. The NI analysis of the primary efficacy endpoint will also be performed using the actual stratification factors (CRF derived) on the PPS Set.

Thirdly, the NI analysis will be repeated on the PP Set with co-infected cases excluded from the analyses:

- co-infection of influenza with COVID-19 and/or respiratory syncytial virus (RSV) as confirmed by the RT-PCR respiratory test panel;
- co-infection of influenza with any other respiratory virus as confirmed by the RT-PCR respiratory test panel.

Co-infections are identified from the same NP swab or two swabs collected within 3 days.

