6.8. Data Safety Monitoring Board

A DSMB will be used throughout the conduct of this study. This committee will be composed of independent members with relevant therapeutic and/or biostatistical expertise

to allow for the ongoing review of safety data from this study population. Safety data will be reviewed according to intervals defined in the DSMB charter and will also occur as needed.

The DSMB will review the IA results and make recommendations to the Sponsor in terms of study results reporting and unblinding based on the boundaries of early efficacy as described in this SAP.

The Sponsor may also request that the DSMB conduct ad hoc reviews of safety events from this study. The DSMB composition, its remit, and frequency of data review will be further defined in the DSMB charter.

7. Changes from Planned Analyses in Protocol

No changes have been made to those analyses planned in the protocol.

8. References

Department of Health and Human Services (DHHS), Food and Drug Administration (FDA), Center for Biologics Evaluation and Research (US). Guidance for industry: Toxicity grading scale for healthy adult and adolescent volunteers enrolled in preventative vaccine clinical trials. September 2007.

Available from:

<https://www.fda.gov/downloads/BiologicsBloodVaccines/GuidanceComplianceRegulatoryInformation/Guidances/Vaccines/ucm091977.pdf>.

9. List of Appendices

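### The protocol gives two censoring times for participants without a case; the SAP keeps one, and no planned analysis tests the effect of lapsed symptom surveillance

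*Protocol*

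**What the plan says.** Protocol 9.5.1.1 first states that "participants without RT-PCR confirmed protocol-defined ILI will be censored at the last study assessment date". Two paragraphs later it states that the same participants "will be censored at Day 181 (Month 6) or end of influenza season (whichever occurs later), or at the date of early discontinuation" or unrelated death, whichever is earlier. Its Kaplan-Meier paragraph follows the second rule: "Participants without a case for the primary endpoint identified will be censored at Day 181/Month 6 or end of influenza season, whichever ends later". The Danish text in Appendix 6 (11.6.1) repeats the second rule as the missing-data description for 9.5.1.1.

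The protocol's estimand table (Appendix 3, Table 10) sides with the first rule: "censoring at early discontinuation, early infection, or last assessment for an event not being observed, whichever comes earlier".

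SAP 6.3.1.2.1 says that participants without a case "will be censored at Day 181 (Month 6) or the end of the influenza season (whichever occurs later), or at the data cutoff date" for the interim analysis, or at early discontinuation or unrelated death, whichever is earliest. SAP Table 10 and Table 14 have no last-assessment term either. SAP Section 1 says that the SAP prevails where the two documents differ. SAP Section 7 says: "No changes have been made to those analyses planned in the protocol".

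On unreachable participants, Protocol 7.2 says: "Should the participant continue to be unreachable, the participant will be considered to have withdrawn from the study". Neither document says what date such a withdrawal carries, and neither ties censoring to a lapse in symptom reporting.

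**The concern.** Two rules for one group cannot both be the primary rule, and the protocol's estimand variable is not the one that the SAP will analyze. The SAP does not acknowledge this.

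Under the SAP rule, only a recorded discontinuation or death removes a non-case before the window end or the interim cutoff. A participant who stops answering the symptom eDiary but is never declared withdrawn, or is declared so late, contributes time at risk in which a case is unlikely to be found. A case needs a positive RT-PCR within 7 days of ILI onset (Protocol 8.10.5), so an illness first mentioned at a later safety call usually comes too late unless it was tested elsewhere. Scheduled safety calls fall at Days 8, 29, 91 and 181. The interim analysis is exposed too, because lapsed participants not yet declared withdrawn by mid-February are censored at the data cutoff.

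If more mRNA-1010 than comparator participants lapse, the hazard ratio falls and noninferiority becomes easier to claim. If fewer lapse, the reverse holds. The planned analyses would not reveal either. The noninferiority sensitivity analyses change the analysis set, the source of the strata or the handling of co-infections, while the incidence-rate and Kaplan-Meier analyses in SAP 6.3.1.2.3 reuse the primary censoring rules.

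**Working it through.** **Design figures, reproduced first.** Inputs from Protocol 9.3 and Table 8: one-sided 2.5%, Lan-DeMets Pocock spending, looks at 274 and 365 PP cases, margin HR 1.1, target HR 0.75.

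- Alpha spent at 75% information: 0.025 × ln(1 + (e − 1) × 0.75) = 2.07%, so z = 2.040.
- Final boundary, with correlation √0.75 between looks: z = 2.258, nominal 1.20%.
- HR boundaries: 1.1 × exp(−2 × 2.040/√274) = 0.860 and 1.1 × exp(−2 × 2.258/√365) = 0.868.
- Power, with drift ln(1.1/0.75) × √d/2: 87.1% at the interim and 93.7% overall.

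All match Protocol Table 8. (SAP Table 5 prints different cumulative probabilities, 78.9% and 95.0%, for the same boundaries. That is a separate matter.)

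**Effect of lapses under the SAP rule.** Let q0 and q1 be the shares of the comparator and mRNA-1010 arms that lapse without being censored. These are assumptions; the documents give none. Assume also that lapses spread evenly over the window, so that a lapsed participant loses on average half of the detectable risk, and that no case is found after a lapse. Detected cases in an arm fall by the factor 1 − q/2, while its time at risk is almost unchanged because cases are rare (2% attack rate). So

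HR observed ≈ HR true × (1 − q1/2)/(1 − q0/2).

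With true HR 1.10, each look's statistic shifts by −ln(multiplier) × √d/2, and the two-look crossing probability is recomputed with the boundaries above.

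| Comparator / mRNA-1010 lapses | Multiplier | HR observed | Type I error |
|---|---|---|---|
| 5% / 5% | 0.975/0.975 = 1.000 | 1.100 | 2.5% |
| 1% / 2% | 0.990/0.995 = 0.995 | 1.094 | 2.8% |
| 5% / 7% | 0.965/0.975 = 0.990 | 1.089 | 3.1% |
| 5% / 10% | 0.950/0.975 = 0.974 | 1.072 | 4.2% |
| 10% / 5% | 0.975/0.950 = 1.026 | 1.129 | 1.4% |

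The factor of one half matters. If every lapse came at the start of the window, 5%/10% would give 0.90/0.95 = 0.947 and a type I error of 6.9%.

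Equal lapses cost cases only. Expected PP cases are 23,000 × 0.9/2 × (0.02 + 0.015) = 362; with 5% lapsing in each arm, 362 × 0.975 = 353.

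**Simulation check.** With 10,350 participants per arm, true HR 1.10 and 5%/10% lapses independent of illness, the SAP rule gave HR 1.073. Censoring at the lapse gave 1.101.

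**The case against.** There is little doubt which rule will be run. The Day 181/season-end paragraph is the specific missing-data text, it recurs for the Kaplan-Meier curve and in Appendix 6, and the SAP follows it closely. Against that paragraph alone, SAP Section 7 is accurate. This stands as far as it goes, but the protocol's other sentence and its estimand table are still current text and say something else.

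A reader might infer that the SAP created the gap by dropping the last-assessment term. The documents do not support that. The protocol never defines a last study assessment, and the safety calls are numbered visits in the Schedule of Events. Someone who ignores the eDiary but takes the Day 181 or Day 361 call would have a late last assessment under the protocol's wording too. Restoring those words would therefore not cure the problem.

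A reader might also infer that everyone who stops responding is counted as event-free. That is too strong. Participants who cannot be reached are treated as withdrawn after due diligence (Protocol 7.2), and withdrawal is a censoring event. Protocol 7.1 uses data up to withdrawal or last contact. Sites follow up missed eDiary entries (8.9.4), and reminders go out weekly to Day 181. Symptoms can be reported by telephone, and an RT-PCR from any setting can count. What remains is those never declared withdrawn and those whose withdrawal is dated late. The plan allows only about 10% for all PP non-evaluability, so residual lapses of 5% to 10% may be high; the 1%/2% row may be nearer.

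Finally, replacing the primary rule with last-contact censoring has its own bias. Cases found after a lapse would still count, while lapsed non-cases would leave the risk set. It also assumes that lapsing is unrelated to illness. This objection stands, and it favors a sensitivity analysis over a new primary rule.

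**Conclusion.** The conflict in the protocol text is real and needs reconciling whatever the lapse rate. The SAP rule leaves a residual group in the risk set without surveillance, and no planned analysis shows how much that matters.

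The documents do not support a claim that the noninferiority test is biased. Equal lapses give no bias. For the assumed differences tabulated above with evenly spread lapses, type I error lies between about 1.4% and 4.2% against the planned 2.5%. Neither document gives a lapse rate, and neither says which arm would lapse more; a link to reactogenicity would be conjecture. The figures also assume that no case is detected after a lapse, which overstates the effect wherever telephone reports or outside RT-PCR results bring cases in.

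This is a cheap improvement to the plan, not a flaw shown to invalidate the primary analysis.

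**What to change.** 1. Reconcile Protocol 9.5.1.1 and its estimand Table 10 with SAP 6.3.1.2.1, Table 10 and Table 14, so that all state one censoring rule for participants without a case. If the Day 181/season-end rule is kept, remove the last-assessment wording.
2. Define the discontinuation date of a participant lost to follow-up as the date of last contact.
3. Prespecify, for both the noninferiority and the superiority test, a sensitivity analysis that censors at the last completed ILI surveillance contact (eDiary entry or call), capped at the window end or data cutoff. Apply the same cut to cases first detected after a lapse, so that censoring does not depend on the outcome.
4. Tabulate symptom-reporting compliance by arm.

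The cost is wording in both documents and one date derived from data already collected. The sensitivity analysis will have slightly less person-time and possibly a few fewer cases.

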9.5.1.2. Analysis of Secondary Efficacy Endpoints

Secondary efficacy endpoints that are defined in [Section 3](#) will be analyzed in a similar way as for the primary efficacy endpoint. More details can be found in the SAP.

9.5.2. Safety Analyses

All safety analyses will be based on the Safety Set, except summaries of solicited ARs, which will be based on the Solicited Safety Set. All safety analyses will be provided by vaccination group.

9.5.2.1. Adverse Events

Safety and reactogenicity will be assessed by clinical review of all relevant parameters, including solicited ARs (local and systemic events), unsolicited AEs, SAEs, MAAEs, AESIs, AEs leading to discontinuation, vital signs, and physical examination findings.

Unsolicited AEs will be coded by system organ class and preferred term according to the MedDRA terminology. The Toxicity Grading Scale for Healthy Adult and Adolescent Volunteers Enrolled in Preventive Vaccine Clinical Trials ([DHHS 2007](#)) will be used in this study.

The number and percentage of participants with any solicited local AR, solicited systemic AR, and any solicited AR during the 7-day follow-up period after the study intervention will be summarized. A 2-sided 95% exact CI using the Clopper-Pearson method will also be provided for the percentage of participants with any solicited AR for each vaccination group.

Number and percentage of participants with unsolicited AEs, SAEs, MAAEs, AESIs, severe AEs, and AEs leading to discontinuation from the study will be summarized. Numbers of events of unsolicited AEs, SAEs, MAAEs, and AESIs will be reported in summary tables accordingly.

For all other safety parameters, descriptive summary statistics will be provided, and [Table 7](#) summarizes analysis strategy for safety parameters. Further details will be described in the SAP.

Table 7: Analysis Strategy for Safety Parameters

Safety Endpoint	Number and Percentage of Participants, Number of Events	95% CI
Any Solicited AR (overall and by local, systemic)	X	X
Any Unsolicited AE	X	
Any SAE	X	
Any AESI	X	
Any Unsolicited MAAE	X	
Any Unsolicited Treatment-Related AE	X	
Any Treatment-Related SAE	X	
Discontinuation due to AE	X	
Any Grade 3 and above AE	X	
Any Treatment-Related Grade 3 and above AE	X	

Abbreviations: AE = adverse event; AESI = adverse event of special interest; AR = adverse reaction; CI = confidence interval; MAAE = medically-attended adverse event; MedDRA = Medical Dictionary for Regulatory Activities; SAE = serious adverse event.

Notes: 95% CI using the Clopper-Pearson method, X = results will be provided. Unsolicited AEs will be summarized by system organ class and preferred term coded by MedDRA.

9.5.2.2. Baseline Descriptive Statistics

Demographic variables (eg, age, sex, race, and ethnicity) and baseline characteristics (eg, height, weight, and body mass index) will be summarized by study intervention group in descriptive statistics (mean, standard deviation for continuous variable, and number and percentage for categorical variables).

9.5.3. Immunogenicity Analyses

The primary analysis population for immunogenicity will be the PP Immunogenicity Subset, unless specified otherwise.

For each of the 4 strains, the GMT of HAI titers with corresponding 95% CI will be provided at each timepoint. The 95% CIs will be calculated based on the *t*-distribution of the log-transformed values then back-transformed to the original scale. The GMFR of HAI titers with corresponding 95% CI at each postbaseline timepoint over baseline will be provided. Descriptive summary statistics including median, minimum, and maximum will also be provided.

An analysis of covariance model will be carried out. The model will include the log-transformed HAI titers at Day 29 as the dependent variable, vaccination group as the fixed variable, log-transformed baseline HAI titers as a fixed covariate, and adjusting for the stratification factors. The geometric least square mean (GLSM) and its corresponding 95% CI results in log-transformed scale estimated from the model will be back-transformed to obtain these estimates in the original scale as an estimate of the GMT. GMR, estimated by the ratio of GLSM and the corresponding 2-sided 95% CI will be provided to assess the treatment difference. The

corresponding 2-sided 95% CI of GMR will be provided to assess the difference in immune response between the mRNA-1010 group compared with the active comparator group at Day 29.

For each strain, seroconversion is defined as either a prevaccination HAI titer < 1:10 and a postvaccination titer \geq 1:40 or a prevaccination HAI titer \geq 1:10 and a minimum 4-fold rise in postvaccination HAI antibody titer.

The number and percentage of participants with seroconversion due to vaccination will be provided with 2-sided 95% CI using the Clopper-Pearson method at Day 29. To compare the seroconversion rates between the vaccination groups, the Miettinen-Nurminen's method will be used to calculate the 95% CI for the difference in seroconversion rates. The seroconversion rate difference with the corresponding 95% CI at Day 29 will be provided for each strain.

For summarizations of GMTs, antibody titers reported as below the lower limit of quantification (LLOQ) will be replaced by $0.5 \times$ LLOQ. Values that are greater than the upper limit of quantification (ULOQ) will be converted to the ULOQ.

In addition, the number and percentage of participants with an HAI titer \geq 1:40 postinjection due to vaccination will be provided with 2-sided 95% CI using the Clopper-Pearson method.

The analyses will be repeated using the Immunogenicity Subset as a sensitivity analysis.

